The following procedures will be conducted at Visit 5 for all subjects:

- Concomitant Medications
- Vital Signs
- Anthropometrics (weight, height, waist circumference, BMI)
- 12-Lead ECG
- PANSS
- CGI-S
- CGI-I

- AE/SAE Assessment
- C-SSRS

Phase 2

Visit 6 (Phase 2 Baseline, Day 13)

The following procedures will be conducted at Visit 6 for all subjects:

- Concomitant Medications
- Vital Signs
- Anthropometrics (weight, height, waist circumference, BMI)
- 12-Lead ECG
- Urine Drug Screen
- PANSS
- CGI-S
- CGI-I
- MATRICS
- UPSA-B
- AE/SAE Assessment
- AIMS
- SAFTEE-SI
- C-SSRS

Visit 7 (Phase 2 Infusion, Day 14)

Anthropometrics, vital signs urinalysis, and concomitant medications will be collected for all subjects at the start of Visit 7 (Hours -1 to 0) prior to initiating the infusion. Subjects will also have blood sample drawn for chemistry and electrolytes. Female subjects of childbearing potential will have a pregnancy test prior to the infusion. If pregnancy test is positive, subject will not continue with the infusion. Subjects who use tobacco will be provided transdermal nicotine in order to prevent withdrawal symptoms. The nicotine replacement will be based on the number of cigarettes per day (cpd) or tobacco equivalent collected at screening.

- ≥ 15 cpd: 21 mg patch
- 8-15 cpd: 14 mg patch
- 5-8 cpd: 7 mg patch
- < 5 cpd: PRN nicotine gum or lozenges 2 mg (1 piece every 3-4 hours)

Intravenous sodium nitroprusside or Placebo infusion will take place during hours 0-4. Cardio-pulmonary monitoring will take place throughout intravenous infusion (see Infusion Monitoring and Discharge Procedures).

Following completion of infusion, the subject will have a post-infusion debrief. The following measurements will be collected for all subjects between hours 4 and 7:

- Vital Signs
- 12-Lead ECG
- AE/SAE Assessment
- AIMS
- SAFTEE-SI
- PANSS
- CGI-S
- CGI-I

Following the completion of all study assessments, a study psychiatrist or nurse practitioner will perform discharge procedures in order release the subject at the end of the visit.

Visit 8 (Phase 2 Follow Up, Day 21)

The following procedures will be conducted at Visit 8 for all subjects:

- Concomitant Medications
- Vital Signs
- Anthropometrics (weight, height, waist circumference, BMI)
- 12-Lead ECG
- PANSS
- CGI-S
- CGI-I
- AE/SAE Assessment
- C-SSRS

Visit 9 (Phase 2 Final Follow Up/Study Completion, Day 28)

The following procedures will be conducted at Visit 9 for all subjects:

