A 10-minute run-in period ("Phase I") has been added to ensure that the patient tolerates the drug. As determined by consulting cardiologist, this will include the administration of the drug at half of the rate (0.25 mcg/kg/min). The following Safety parameters will be followed for Phase I:

Safety Parameters

Safety Parameters Phase I dose:

- If SBP \leq 89 STOP infusion. Lie flat, feet up, call N.P. & P.I.
- If HR $>$ 120 bpm or $>$ 20 bpm over baseline HR, abort study
- If SpO2 $<$ 92%, stop infusion
- If patient reports headache, ask: "do you feel this headache is tolerable?"
 - If patient says "yes," continue dose
 - If patient says "no," STOP dose

-If patient experiences symptomatic hypotension (nausea, dizziness) STOP infusion.

If Phase I is tolerated per the above guidelines after the 10 minute run-in period, the drug will be administered at the rate of 0.5 mcg/kg/min ("Phase II") with the following parameters:

Safety Parameters for Phase II dose:

- If SBP between 81 and 89, lower dose to Phase I dose for 15 min. Monitor with CRC NP.
- If SBP rises to > 89mm Hg continue Phase I dose
- If SBP remains between 81 and 89mm Hg abort and call P.I.
- If SBP < 80, STOP infusion, lie flat, feet up & call P.I.
- If HR > 120 bpm or > 20 bpm over baseline HR, lower dose to Phase I dose for 15 min
- If SpO2 < 92% Stop infusion
- If patient reports headache, ask, "Do you feel this headache is tolerable?"
 - If patient says "yes", continue dose
 - If patient says "no", *lower dose to Phase I dose for 15 min*
- If better, continue Phase I dose
- If still intolerable, STOP dose
- If patient experiences symptomatic hypotension (nausea, dizziness) *lower dose to Phase I dose for 15 min*
- If better, continue Phase I dose
- *If not, Stop infusion, call P.I.*

Should the patient require PRN rescue medications, the following procedures will take place:

PRN Rescue medications:

In consultation with CRC N.P.

For SBP < 80 mmHg, may give 250 ml 0.9% NS

IV bolus via Sigma pump @999 ml/hr over 15 min X 2

For rash may give

Diphenhydramine 25 mg by mouth X 1

The IV line will be left in place for at least 1 hour following the infusion to allow for additional medications to control emergent side effects. If additional IV medication is necessary, an anesthesiologist, cardiologist, or medically qualified designate will start the infusion and a medical team will be present during the entire infusion period.

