The hypotensive effect of sodium nitroprusside is augmented by that of most other hypotensive drugs, including ganglionic blocking agents, negative inotropic agents, and inhaled anesthetics. Subjects taking any of these drugs will be excluded from the study.

Concomitant Therapy

The subject may not have adjustment of psychotropic medications except for benzodiazepines or anticholinergic agents if deemed absolutely necessary by the Investigator for relief of transient symptoms. (See Appendix 3: Medications Allowed and Not Allowed as Concomitant Medications). Subjects must be questioned at each study visit concerning any new medications or changes in current medications including over-the-counter medication and topical medication. All medications and therapies administered or taken by the subject beginning 30 days prior to signing the ICF and throughout the study will be recorded. The subjects' antipsychotic medication type should have remained unchanged for at least eight (8) weeks prior to screening into the study, at constant dose for at least 4 weeks, and should be expected to remain unchanged during the study.

For each medication and non-study treatment, the following will be documented:

- Medication/treatment name (generic name may be used if trade name is unknown)
- If an anti-psychotic medication, whether typical or atypical.
- Dose, unit, and frequency of dosing (individual dosages, not total daily dose). Note: Each new dose of medication should be recorded as a separate entry, with the exception of medications that are given on a sliding scale. For these, it is acceptable to enter the range of the dosage, including the start and stop dates for which the specified dosage range was used.
- Route of dosing
- Indication for use
- The start date
- The stop date (if medication/therapy is not ongoing)

Discontinuation from Study Treatment

Every effort will be made to keep the patient in the study for the full study period consisting of two phases of treatment with follow-up assessments. Acceptable reasons for early discontinuation include the following: 1) request of patient, 2) decision of physician, 3) serious adverse event, and 4) protocol violation.

Medical Reasons for Discontinuation:

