Treatment (infusion) discontinuation will be determined by the criteria outlined in the Infusion Monitoring and Discharge Procedures section of this Protocol. A study physician will be available for consultation on any participant safety issues that arise during the infusion.

A patient who decides to discontinue participation in the study will always be asked about the reason(s) and the presence of any AEs. If possible, they will be seen and assessed by an investigator. AEs will be followed up until resolution.

Procedures for Discontinuation from Study:

If a patient discontinues from the study before randomization, then no further follow-up will be expected. However, if the patient discontinues after randomization, but before receiving any study treatment, the patient will be asked to return for a final study visit, during which the procedures outlined in the Visit 9 Final Visit/Early Termination Visit procedures will be completed, including AEs and concomitant medication assessments.

If a patient discontinues from the study before completion and has received the dose of study drug, the patient will be asked to return for a final study visit, at which the procedures outlined in the Early Termination Visit will be completed. Every effort should be made to follow up with patients who discontinue from the study prior to Visit 9 (Day 28). If patients refuse to return to the clinic for the study-related assessments, a modified follow-up through, for example, regular telephone contact or a contact at study closure should be arranged, if agreed to by the patient and in compliance with local data privacy laws/practices. If the patient refuses follow-up, the reason for the refusal and last contact date should be documented in the eCRF and source documents.

Patients who discontinue from the study will not be replaced.

If an Early Termination Visit is warranted, the following procedures will be performed:

- Concomitant medications
- Vital Signs
- 12-lead ECG
- Anthropometrics (weight, height, waist circumference, BMI)
- CBC with differential and Comprehensive Metabolic Panel (CMP)
- Urinalysis
- Serum Pregnancy test
- PANSS
- CGI-S

- CGI-I
- AE/SAE assessment
- AIMS
- SAFTEE
- C-SSRS
- MATRICS
- UPSA-B

Unblinding Procedure

Methods for Ensuring Blinding

The investigator, subject, and study staff will be blinded. The preparation and labeling of the study drugs will be performed by the site pharmacy in a way to ensure blinding throughout the study.

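### The infusion stop rules do not say what each stop ends, so the second infusion and later PANSS ratings of a stopped subject depend on how the site reads them

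*Protocol*

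**What the plan says.** Infusion Monitoring and Discharge Procedures (Protocol, section H) has two lists of Safety Parameters: one for a 10-minute run-in at half rate, one for the full rate. The lists call these steps Phase I and Phase II. Elsewhere, Phase 1 and Phase 2 are the two-week periods that follow the Day 0 and Day 14 infusions.

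The lists word the outcome in four ways: *STOP infusion*, *STOP dose*, *abort* and *abort study*. At full rate they say "If SBP < 80, STOP infusion, lie flat, feet up & call P.I" and "If SBP remains between 81 and 89mm Hg abort and call P.I". The run-in heart-rate line ends "20 bpm over baseline HR, abort study". None of the four terms is defined.

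In section I, Medical Reasons for Discontinuation says: "Treatment (infusion) discontinuation will be determined by the criteria outlined in the Infusion Monitoring and Discharge Procedures section of this Protocol". Discontinuation from Study Treatment begins "Every effort will be made to keep the patient in the study for the full study period consisting of two phases of treatment", and then names physician decision and a serious adverse event among the acceptable reasons for leaving early.

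Study Design schedules an infusion on Day 0 and Day 14 for every subject, active on both days for the 20 drug-drug subjects. The Visit 7 procedures state one bar to the Day 14 infusion: "If pregnancy test is positive, subject will not continue with the infusion".

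**The concern.** A site that stops a Day 0 infusion has two questions that the text does not answer: is this subject infused on Day 14, and do the PANSS ratings continue? Sites may handle the same event differently.

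The statistical stake is the primary endpoint, the change in PANSS total after two weeks in each stage. If some triggers are read as withdrawal, subjects leave because of a reaction to the infusion, and scheduled ratings go missing for a reason probably related to treatment. The safety stake is that the status of the second infusion after a first one was stopped is left to individual judgement, with no stated criterion and no place to document the decision.

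**Working it through.** No calculation decides this point. The check is to set the rules side by side, follow each reading through to the PANSS data, and then size what can be sized.

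**1. Scope of each trigger**

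| Step | Trigger | Stated outcome | What it ends |
|---|---|---|---|
| Run-in | SBP 89 or less | *STOP infusion* | that infusion; Day 14 not addressed |
| Run-in | heart rate | *abort study* | undefined: session or participation |
| Full rate | SBP stays 81 to 89 after the rate is lowered | *abort*, no object | undefined |
| Full rate | SBP below 80 | *STOP infusion* | that infusion; Day 14 not addressed |
| Full rate | heart rate, same thresholds | lower the rate | nothing ends |
| Both | intolerable headache | *STOP dose* (at full rate, only after the rate is lowered) | undefined |

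Dose Modification during Treatment agrees that SBP below 80 ends the infusion. Medical Reasons for Discontinuation treats the whole set as grounds for ending an infusion, which does not fit *abort study* read literally.

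**2. Consequence for PANSS**

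- *Abort means the session ends.* The subject stays in the study, with PANSS on Days 7, 13, 14, 21 and 28.
- *Abort means withdrawal.* Procedures for Discontinuation from Study gives an Early Termination Visit, which includes PANSS but is not tied to Day 14 or Day 28. Procedure for Non-Compliant Subjects keeps contact for 30 days after treatment for the stated purpose of collecting safety data.

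On the second reading, a Day 0 abort loses the scheduled Day 7 and end-of-Phase-1 PANSS from the Stage 1 comparison. A Day 14 abort in a placebo non-responder given nitroprusside loses Day 21 and Day 28 from the Stage 2 comparison. Drug-drug subjects are not in the Stage 2 comparison, so a Day 14 event in that group does not affect it.

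**3. Size**

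The plan's own figures reproduce. Stage 2 per arm: 20 × 0.8 (20% attrition) × 0.7 (30% placebo response) = 11.2, given as about 11. For power, with SD 14, effects of 9 and 11 and weight 0.5:

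SE = √[0.25 × 14² × (1/20 + 1/40) + 0.25 × 14² × (2/11.2)] = √(3.675 + 8.75) = 3.525

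Power = Φ(10/3.525 − 1.96) = 81.0%, against 81% stated.

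This calculation takes no losses from Stage 1. With 20% removed there (16 and 32 subjects), power is 78.2%. Lost precision is therefore minor; the issue is loss that differs by arm.

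One lost subject is 1/20 = 5% of the Stage 1 active arm, or 1/11 = 9% of the Stage 2 active arm.

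The documents give no stop rate. The prior exposure cited at this rate in schizophrenia is 10 treated subjects with no adverse effects. Zero of 10 gives an upper limit of 1 − 0.05^(1/10) = 26% (one-sided 95%) or 1 − 0.025^(1/10) = 31% (two-sided). These limits concern reported adverse effects, not stops under these rules. For assumed stop rates p:

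| p (assumed) | expected of 20, 20p | at least one of 20, 1 − (1 − p)^20 | expected of 11, 11p |
|---|---|---|---|
| 1% | 0.2 | 18% | 0.1 |
| 5% | 1 | 64% | 0.6 |
| 10% | 2 | 88% | 1.1 |
| 20% | 4 | 99% | 2.2 |

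These count every stop. Only stops read as an abort of the study would cost PANSS data, so the data loss is smaller than the table shows.

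**The case against.** A reader might infer that a subject stopped for hypotension on Day 0 must be re-infused on Day 14 with nothing to guard against toxicity. The documents do not support that:

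- Visit 7 refers back to the same monitoring section, so the run-in and every stop rule apply again.
- The SBP stops require a call to the investigator.
- The medical monitor receives all safety data within 24 hours of each infusion and reviews adverse events throughout.
- A physician can end participation, and blinding does not prevent that.

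That the subject remains due for the second infusion is inferred from the default schedule and from silence; it is not a stated rule.

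A reader might also infer that the rules are ordered backwards, with heart rate treated more severely than low pressure. That holds only within the run-in, and only if *abort study* means withdrawal. At full rate the heart-rate rule is "If HR > 120 bpm or > 20 bpm over baseline HR, lower dose to Phase I dose for 15 min", while SBP below 80 stops the infusion.

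On the data, the Early Termination Visit includes PANSS, and the protocol asks for every effort to follow subjects who leave before Day 28. Its mention of returning to the clinic for study assessments could be read as continued rating. The repeated-measures model would also use whatever ratings exist.

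These points remove the strong safety reading. They leave two gaps. The discretionary safeguards do not say what a Day 0 stop means for Day 14. The follow-up text neither names PANSS at the scheduled visits nor reconciles itself with the sentence that limits continued contact to safety data. The Protocol leaves the missing-data method to the SAP, and the SAP's Missing data section repeats that deferral, so no stated method covers the loss.

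**Conclusion.** The point holds as one of undefined scope with a consequence for the primary data. The terms differ, section I does not resolve them, and no stated rule connects a Phase 1 stop to the Phase 2 infusion. If *abort study* is read as withdrawal, scheduled PANSS is lost at Days 7 and 14 among about 20 active subjects in Stage 1, and at Days 21 and 28 among about 11 in the Stage 2 active arm.

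That losses would fall more on nitroprusside is a judgement: the triggers are mainly circulatory and the drug is a vasodilator, but heart rate can also rise on placebo. How many subjects would be affected, and the size of any bias, cannot be derived from the documents. The stop rates above are assumptions, and with a rate near 1% there may be no case at all. The change is worth making because it costs very little, not because a large effect has been shown.

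**What to change.** The sponsor should reconcile Infusion Monitoring and Discharge Procedures, Dose Modification during Treatment, Discontinuation from Study Treatment, and the medical-reasons and procedures text on discontinuation. Two things should then be explicit:

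- for each trigger, whether it ends that infusion, also the second infusion, or participation;
- the status of the Day 14 infusion after a Day 0 stop.

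Which scope belongs to which trigger is a clinical matter for the investigators and the consulting cardiologist. Using different names for the rate steps and the treatment periods would help.

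Separately, state that a subject whose infusion is stopped, or whose second infusion is not given, stays on the planned PANSS schedule to Day 14 and Day 28 unless consent is withdrawn. Align the safety-only wording in Procedure for Non-Compliant Subjects with that.

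The cost is a few lines of text and continued rating of a few subjects at visits already scheduled.

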In accordance with International Conference on Harmonization (ICH) and Food and Drug Administration (FDA) guidance, any study related event incurred by a subject that occurs after the first study-related procedure to the completion of the protocol-defined safety surveillance period, that represents a change (positive or negative) in frequency or severity from a baseline (pre-study) event (if any), regardless of the presence of causal relationship or medical significance, is a reportable AE.

Abnormal results of diagnostic procedures, including laboratory test abnormalities, are considered AEs if they:

- Result in discontinuation from the study,
- Require treatment or any other therapeutic intervention,

- Require further diagnostic evaluation (excluding a repetition of the same procedure to confirm the abnormality), or
- Are associated with clinical signs or symptoms that would have a significant clinical impact, as determined by the PI.

Performing Adverse Events Assessments

The PI is ultimately responsible for assessing and reporting all adverse events as outlined in the protocol. The assessment of AEs may be delegated to a medically qualified Sub-Investigator, trained on this study protocol, who is listed on the FDA Form 1572 or equivalent document, and on the delegation of authority form.

AEs should be volunteered by the subject, or solicited from the subjects using a standard statement, from examination of the subject at a clinic visit, or from observations of clinically significant lab values or special exam abnormal values. AEs will not be solicited by the use of a specific list of anticipated events.

All AEs are to be assessed and recorded in a timely manner and followed to resolution or until the Investigator determines that there is not an anticipated resolution. Each AE is to be documented with reference to severity, date of occurrence, duration, treatment, and outcome. Furthermore, each AE is to be classified as being serious or non-serious (as per definitions). In addition, the PI or delegated medically qualified Sub-Investigator must assess whether the AE is drug-related or not. Changes in severity of AEs and resolution dates should be documented as separate events.

Timing

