AEs will be captured from the first study-related procedure through to the completion of the protocol defined safety surveillance period. For the purposes of this study, the period of observation for collection of AEs extends from the time the subject gives informed consent until the final visit.

Surgical procedures, planned before enrollment of the subject in the study, are not considered AEs if the condition was known before study inclusion. In this case the medical condition should be reported in the subject's medical history. Intermittent adverse events will not be reported as multiple adverse events. The definition of an intermittent adverse event is "a recurring event of consistent severity, frequency, and causality."

Severity

Each AE is to be documented with reference to severity. Changes in severity of AEs and resolution dates should be documented as separate events. Any event that ameliorates over more than one assessment time point may be considered for listing as a single event at the highest severity.

Table 2. Definition of Intensity of Adverse Events

Intensity	Definition
Mild	Causes transient or mild discomfort; no limitation of usual activities; no medical intervention required.
Moderate	Causes mild to moderate limitation in activity; some limitation of usual activities; no or minimal medical intervention or therapy is required.
Severe	Causes marked limitation in activity; some assistance is usually required; medical intervention or therapy is required; hospitalization is probable.

The term “severe” is often used to describe the intensity (severity) of a specific event (as in mild, moderate, or severe); the event itself, however, may be of relatively minor medical significance (such as a severe headache). This is not the same as “serious,” which is based on subject/event outcome or action criteria usually associated with events that pose a threat to a subject’s life or functioning. Seriousness (not severity) serves as a guide for defining regulatory reporting obligations.

Relationship

The PI or a medically qualified Sub-Investigator, trained on this study protocol, listed on the 1572 or equivalent document and on the delegation of authority form, is responsible for determining the adverse event relationship to the investigational product.

The following categories will be used to define the relationship of an AE to the administration of the IMP:

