In the event of a SAE, the PI or designate will notify the MGH-CTNI Medical Monitor by phone or email within 24 hours of the event and will email supporting documentation

within 48 hours of the event and then as relevant data is available within the following week.

The PI must inform the IRB immediately regarding any AE (does not have to be causally related) that is both serious and unexpected; or that represents a series of AEs that, on analysis, is unanticipated, or occurs at an unanticipated frequency, or otherwise represents an unanticipated safety risk to the study subject. The IRB may subsequently choose to modify the informed consent or request changes to the protocol.

Treatment-Emergent Adverse Events

A treatment emergent adverse event (TEAE) is an AE that either began following initiation of study treatment or was present prior to the initiation of the treatment, but increased in frequency or severity following initiation treatment, regardless of causality.

All TEAEs (post infusion) will be captured on the subject source documents for all required assessments and data transferred to the eCRF. The reporting PI or medically qualified Sub-Investigator will sign and date the source document and eCRF.

Procedures and follow-up of Subjects Experiencing AEs after Completion of or Withdrawal from the Study

If a subject experiences the onset of a SAE within a period of 30 days following study completion and, in the opinion of the PI or medically qualified Sub-Investigator, it is associated with the study, it will be followed up and reported as described above.

Protocol Waivers and Violations

Protocol Waivers

Protocol waivers will be assessed on a case by case basis by the medical monitor and the principle investigator for this study.

Procedure for Non-Compliant Subjects

Subjects who miss a study visit will be allowed (at the discretion of the PI) to make up that visit the next day. Subjects who miss more than one visit will be discontinued from the study. Subjects who withdraw consent will no longer have data collected for the study. Every effort will be made to maintain contact with patients who are discontinued, but who do not withdraw consent, according to the study schedule for 30 days post-treatment in order to collect safety data.

Protocol Deviation and Violation Definitions

Protocol violations as defined in the table below will be reported as described in the Manual of Operations.

Table 3. Major and Minor Protocol Violations

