## **Safety Analyses**

### Adverse Events

Adverse events will be coded using MedDRA. Treatment Emergent AE's (TEAE) are defined as events with an onset on or after the first randomized treatment. TEAEs will be summarized by treatment group and by stage of the study, System Organ Class, and preferred term. The following TEAE summaries will be provided:

- TEAEs by severity grade
- TEAEs by relationship to study treatment.

In addition, separate summaries of serious adverse events, and adverse events resulting in discontinuation of study treatment will be presented.

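### Adverse events include improvement, severity changes are logged as separate events, and two TEAE definitions conflict, so an easing stage 1 event can be tabulated in stage 2

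*Protocol*

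**What the plan says.** Protocol section H, Evaluation of Adverse Events, sets four rules.

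- **Definition.** An event is reportable if it is one "that represents a change (positive or negative) in frequency or severity from a baseline (pre-study) event (if any". Both directions of change are included.
- **Recording** (Performing Adverse Events Assessments, repeated under Severity). "Changes in severity of AEs and resolution dates should be documented as separate events". Each adverse event also carries its own date, duration, severity, treatment and outcome.
- **Easing events** (Severity). "Any event that ameliorates over more than one assessment time point may be considered for listing as a single event at the highest severity". This is permissive and directly follows the separate-events instruction.
- **Intermittent events** (Timing). "Intermittent adverse events will not be reported as multiple adverse events", where intermittent means recurring with consistent severity, frequency and causality.

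Two definitions of a treatment-emergent adverse event (TEAE) follow. Section H, Treatment-Emergent Adverse Events, admits an event that began after study treatment started, or one that "was present prior to the initiation of the treatment, but increased in frequency or severity following initiation treatment, regardless of causality". Protocol section M and the SAP, both under Safety Analyses, Adverse Events, say instead that TEAEs "are defined as events with an onset on or after the first randomized treatment". The SAP then states: "TEAEs will be summarized by treatment group and by stage of the study, System Organ Class, and preferred term". Tables by severity grade and by relationship to treatment are also planned. TEAE incidence is the first item listed under Safety Assessments.

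**The concern.** Safety and tolerability is the trial's secondary objective, and the TEAE tables are its main evidence. The design makes stage attribution matter. In the placebo-drug sequence the treatment switches at Day 14, so whether a record belongs to stage 1 or stage 2 decides whether it is a placebo event or a nitroprusside event.

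The recording rules can create a new record when an existing symptom merely eases or resolves. The analysis definition does not ask whether the record represents worsening. If such a record takes its own date and is placed in the stage where that date falls, a fading placebo event enters the stage 2 nitroprusside column without any new harm. Because the single-listing option is discretionary, two sites can also turn the same clinical course into different numbers of records, and one episode can occupy several rows of the severity table.

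**Working it through.** There is no stated figure to reproduce. The check sets the rules side by side and follows one case through them.

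**Case.** A placebo-drug subject has moderate insomnia starting on Day 3 (stage 1, placebo). It eases to mild on Day 15, the day after the stage 2 infusion, and later resolves.

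**Step 1, number of records.**
- Onset, severity change and resolution each logged: 1 + 1 + 1 = 3.
- Only the severity change adds a record: 1 + 1 = 2.
- Optional single listing used: 1.

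All three readings can be defended from section H. The intermittent-event rule does not help, because it requires consistent severity.

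**Step 2, is the Day 15 record treatment-emergent?**
- *Section M and SAP:* yes, if the record carries its own date as onset, since Day 15 is after the first randomized treatment. There is no direction condition.
- *Section H:* the record does not qualify if the insomnia is treated as present before the stage 2 treatment, because it did not increase. However, that definition is tied to the start of study treatment, which is Day 0. The Day 3 insomnia is therefore already a TEAE under both definitions, and neither settles whether its easing counts again in stage 2.

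**Step 3, which stage?** The SAP tabulates by stage but gives no rule for assigning a record to a stage or for linking records of one episode. Placing the Day 15 record in stage 2 is the natural reading of a separately dated event, but it is not written.

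**Step 4, illustrative size.** Let k of the 20 placebo-drug subjects have a stage 1 event that eases after Day 14, with the follow-on record taking its own date. The added stage 2 incidence in that sequence is k/20:
- k = 1: 1/20 = 5%
- k = 2: 2/20 = 10%
- k = 4: 4/20 = 20%

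The values of k are assumptions. With the section H condition applied at the stage 2 infusion, the figure is 0%.

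**Step 5, effect of the counting unit.** The documents do not say whether incidence counts subjects or events. Counting each subject once per preferred term within a stage removes duplicates inside that stage. The carry-over from stage 1 to stage 2 remains.

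**Step 6, severity table.** On the three-grade scale in the Protocol's intensity table, the insomnia appears under moderate and again under mild unless the records are collapsed to the maximum grade.

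**The case against.** A reader might infer that every easing or resolving symptom becomes a TEAE of that stage's treatment, so that benefit from the drug is tabulated as harm. The documents do not support this.

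- Section H's own TEAE definition excludes a pre-existing event that did not increase. Pre-study headaches that lessen after an infusion are therefore not treatment-emergent on that definition. They become so only if section M and the SAP are read alone and an easing is treated as an onset.
- For symptoms found on the SAFTEE-SI, section H tells the physician to look for worsening of a pre-existing condition or an unfavorable new finding. That is directional, although limited to that instrument.
- An easing event may be listed once at its highest grade, so separate records are not inevitable.
- No text gives a follow-on record its onset date or its stage.
- The subject in the worked case is already a TEAE case from Day 3. Only the split by stage changes.

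A reader might also infer a bias against the drug. That does not follow either. The placebo-drug and placebo-placebo sequences have 20 subjects each, and fading stage 1 placebo events could enter stage 2 from both in similar measure. Grade changes after Day 14 also include true worsening, which belongs in the table.

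These points stand. They reduce the claim from what will happen to what the written rules permit. They do not reconcile the two TEAE definitions, make the single-listing option mandatory, or supply a stage rule.

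**Conclusion.** The point holds as a conflict among stated rules. Improvement lies within the adverse-event definition, severity changes and resolutions are to be separate events with only an optional collapse, and the analysis definition lacks the direction condition that section H imposes. Followed literally, these rules can place an easing stage 1 placebo event in the stage 2 table, including the nitroprusside column for the 20 placebo-drug subjects, and can spread one episode over several severity grades.

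That result needs three conditions: the site does not use the single-listing option, the follow-on record takes its own post-infusion date, and the onset-only definition governs. How often they coincide cannot be derived from the documents, so the 5% to 20% range is illustrative only. The effect is confined to the safety summaries; the primary efficacy test is untouched. Correction is worthwhile because the first listed safety endpoint is affected and the remedy is cheap.

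**What to change.** 1. In the Protocol section H definition, limit adverse events to new or worsened events.
2. Use one TEAE definition in Protocol sections H and M and in the SAP: onset after the infusion of that stage, or worsening above the grade held before it.
3. State in the SAP that each TEAE belongs to the stage of the infusion preceding its onset or worsening.
4. Link severity-change and resolution records to their parent episode, and state that improvement or resolution never creates a TEAE.
5. Count each subject once per preferred term per stage, at maximum severity.

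The severity-change records need not be dropped. Kept as linked records and collapsed at analysis, they preserve the time course. The cost is wording in the two documents, matching eCRF guidance and a link between records of one episode. No new assessments or data are required.
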